#### **9.1.3. Informed Consent**

The investigator is responsible for obtaining written informed consent from each individual participating in this study after adequate explanation of the aims, methods, objectives, and potential hazards of the study and before undertaking any study-related procedures. The investigator must use the most current IRB/IEC approved consent form for documenting written

informed consent. Each informed consent (or assent as applicable) will be appropriately signed and dated by the subject or the subject's legally authorized representative and the person conducting the consent discussion, and also by an impartial witness if required by IRB/IEC or local requirements. The consent form will inform subjects about genomic testing and sample retention.

#### **9.1.4. Confidentiality**

The investigator must assure that subjects' anonymity will be strictly maintained and that their identities are protected from unauthorized parties. Only subject initials, date of birth, another unique identifier (as allowed by local law) and an identification code will be recorded on any form or biological sample submitted to the Sponsor, IRB/IEC, or laboratory. Laboratory specimens must be labeled in such a way as to protect subject identity while allowing the results to be recorded to the proper subject. Refer to specific laboratory instructions or in accordance with local regulations. NOTE: The investigator must keep a screening log showing codes, and names for all subjects screened and for all subjects enrolled in the trial. Subject data will be processed in accordance with all applicable regulations.

The investigator agrees that all information received from Gilead, including but not limited to the IB, this protocol, eCRF, the IMP, and any other study information, remain the sole and exclusive property of Gilead during the conduct of the study and thereafter. This information is not to be disclosed to any third party (except employees or agents directly involved in the conduct of the study or as required by law) without prior written consent from Gilead. The investigator further agrees to take all reasonable precautions to prevent the disclosure by any employee or agent of the study site to any third party or otherwise into the public domain.

#### **9.1.5. Study Files and Retention of Records**

The investigator must maintain adequate and accurate records to enable the conduct of the study to be fully documented and the study data to be subsequently verified. These documents should be classified into at least the following two categories: (1) investigator's study file, and (2) subject clinical source documents.

The investigator's study file will contain the protocol/amendments, eCRF and query forms, IRB/IEC and governmental approval with correspondence, informed consent, drug records, staff curriculum vitae and authorization forms, and other appropriate documents and correspondence.

The required source data should include sequential notes containing at least the following information for each subject:

- Subject identification (name, date of birth, gender);
- Documentation that subject meets eligibility criteria, ie, history, PE, and confirmation of diagnosis (to support inclusion and exclusion criteria);
- Documentation of the reason(s) a consented subject is not enrolled;

- Participation in study (including study number);
- Study discussed and date of informed consent;
- Dates of all visits;
- Documentation that protocol specific procedures were performed;
- Results of efficacy parameters, as required by the protocol;
- Start and end date (including dose regimen) of IMP, including dates of dispensing and return;
- Record of all AEs and other safety parameters (start and end date, and including causality and severity);
- Concomitant medication (including start and end date, dose if relevant; dose changes);
- Date of study completion and reason for early discontinuation, if it occurs.

All clinical study documents must be retained by the investigator until at least 2 years or according to local laws, whichever is longer, after the last approval of a marketing application in an ICH region (ie, US, Europe, or Japan) and until there are no pending or planned marketing applications in an ICH region; or, if no application is filed or if the application is not approved for such indication, until 2 years after the investigation is discontinued and regulatory authorities have been notified. Investigators may be required to retain documents longer if specified by regulatory requirements, by local regulations, or by an agreement with Gilead. The investigator must notify Gilead before destroying any clinical study records.

Should the investigator wish to assign the study records to another party or move them to another location, Gilead must be notified in advance.

If the investigator cannot provide for this archiving requirement at the study site for any or all of the documents, special arrangements must be made between the investigator and Gilead to store these records securely away from the site so that they can be returned sealed to the investigator in case of an inspection. When source documents are required for the continued care of the subject, appropriate copies should be made for storage away from the site.

#### **9.1.6. Case Report Forms**

For each subject consented, an eCRF will be completed by an authorized study staff member whose training for this function is documented according to study procedures. The eCRF should be completed on the day of the subject visit to enable the sponsor to perform central monitoring of safety data. The Eligibility Criteria eCRF should be completed only after all data related to eligibility have been received. Subsequent to data entry, a study monitor will perform source data verification within the electronic data capture (EDC) system. Original entries as well as any changes to data fields will be stored in the audit trail of the system. Prior to database lock (or any

interim time points as described in the clinical data management plan), the investigator will use his/her log in credentials to confirm that the forms have been reviewed, and that the entries accurately reflect the information in the source documents. The eCRF captures the data required per the protocol schedule of events and procedures. System-generated or manual queries will be issued to the investigative site staff as data discrepancies are identified by the monitor or internal Gilead staff, who routinely review the data for completeness, correctness, and consistency. The site coordinator is responsible for responding to the queries in a timely manner, within the system, either by confirming the data as correct or updating the original entry, and providing the reason for the update (eg, data entry error). At the conclusion of the trial, Gilead will provide the site with a read-only archive copy of the data entered by that site. This archive must be stored in accordance with the records retention requirements outlined in Section 9.1.5.

#### **9.1.7. Investigational Medicinal Product Accountability and Return**

Where possible, IMP should be destroyed at the site. At the start of the study, the study monitor will evaluate each study center's IMP disposal procedures and provide appropriate instruction for disposal or return of unused IMP supplies. If the site has an appropriate standard operating procedure (SOP) for drug destruction as determined by Gilead Sciences, the site may destroy used (empty or partially empty) and unused IMP supplies as long as performed in accordance with the site's SOP. This can occur only after the study monitor has performed drug accountability during an on-site monitoring visit.

A copy of the site's IMP Disposal SOP or written procedure (signed and dated by the Principal Investigator [PI] or designee) will be obtained for Gilead site files. If the site does not have acceptable procedures in place, arrangements will be made between the site and Gilead Sciences (or Gilead Sciences' representative) for return of unused study drug supplies.

If IMP is destroyed on site, the investigator must maintain accurate records for all IMPs destroyed. Upon study completion, copies of the IMP accountability records must be filed at the site. Another copy will be returned to Gilead.

The study monitor will review IMP supplies and associated records at periodic intervals.

#### **9.1.8. Inspections**

The investigator will make available all source documents and other records for this trial to Gilead's appointed study monitors, to IRBs/IECs, or to regulatory authority or health authority inspectors.

#### **9.1.9. Protocol Compliance**

The investigator is responsible for ensuring the study is conducted in accordance with the procedures and evaluations described in this protocol.

## **9.2. Sponsor Responsibilities**

### **9.2.1. Protocol Modifications**

Protocol modifications, except those intended to reduce immediate risk to study subjects, may be made only by Gilead. The investigator must submit all protocol modifications to the IRB/IEC in accordance with local requirements and receive documented IRB/IEC approval before modifications can be implemented.

### **9.2.2. Study Report and Publications**

A clinical study report (CSR) will be prepared and provided to the regulatory agency(ies). Gilead will ensure that the report meets the standards set out in the ICH Guideline for Structure and Content of CSRs (ICH E3). Note that an abbreviated report may be prepared in certain cases.

Investigators in this study may communicate, orally present, or publish in scientific journals or other scholarly media only after the following conditions have been met:

- The results of the study in their entirety have been publicly disclosed by or with the consent of Gilead in an abstract, manuscript, or presentation form or the study has been completed at all study sites for at least 2 years
- The investigator will submit to Gilead any proposed publication or presentation along with the respective scientific journal or presentation forum at least 30 days before submission of the publication or presentation.
- No such communication, presentation, or publication will include Gilead's confidential information (See Section 9.1.4).
- The investigator will comply with Gilead's request to delete references to its confidential information (other than the study results) in any paper or presentation and agrees to withhold publication or presentation for an additional 60 days in order to obtain patent protection if deemed necessary.

## **9.3. Joint Investigator/Sponsor Responsibilities**

### **9.3.1. Payment Reporting**

Investigators and their study staff may be asked to provide services performed under this protocol, eg, attendance at Investigator's Meetings. If required under the applicable statutory and regulatory requirements, Gilead will capture and disclose to Federal and State agencies any expenses paid or reimbursed for such services, including any clinical trial payments, meal, travel expenses or reimbursements, consulting fees, and any other transfer of value.

### **9.3.2. Access to Information for Monitoring**

In accordance with regulations and guidelines, the study monitor must have direct access to the investigator's source documentation in order to verify the accuracy of the data recorded in the eCRF.

The monitor is responsible for routine review of the eCRF at regular intervals throughout the study to verify adherence to the protocol and the completeness, consistency, and accuracy of the data being entered on them. The monitor should have access to any subject records needed to verify the entries on the eCRF. The investigator agrees to cooperate with the monitor to ensure that any problems detected through any type of monitoring (central, on site) are resolved.

### **9.3.3. Access to Information for Auditing or Inspections**

Representatives of regulatory authorities or of Gilead may conduct inspections or audits of the clinical study. If the investigator is notified of an inspection by a regulatory authority the investigator agrees to notify the Gilead medical monitor immediately. The investigator agrees to provide to representatives of a regulatory agency or Gilead access to records, facilities, and personnel for the effective conduct of any inspection or audit.

### **9.3.4. Study Discontinuation**

Both the sponsor and the investigator reserve the right to terminate the study at any time. Should this be necessary, both parties will arrange discontinuation procedures and notify the appropriate regulatory authority(ies), IRBs, and IECs. In terminating the study, Gilead and the investigator will assure that adequate consideration is given to the protection of the subjects' interests.

**Appendix 2. Study Procedures Table**

Period	Screen	Treatment																			Follow-up	
		1	2	3	4	5	6	7	8	9	10	11	12	13	14	15	16	17	18	19	20	PTx a
Visit	1	2	3	4	5	6	7	8	9	10	11	12	13	14	15	16	17	18	19	20		
Week		0	2	4	6	10	11	14	17	20	23	26	30	34	38	42	46	50	54	58		
Study Day	-30 to -1	1	15	29	43	71	78	99	120	141	162	183	211	239	267	295	323	351	379	407		
Visit Window			±3	±3	±3	±2	±3	±5	±5	±5	±5	±5	±5	±5	±5	±5	±5	±5	±5	±5	±3	±3
Written Informed Consent	X																					
Medical History & Demographics	X																					
Ulcerative Colitis Treatment History and disease extent	X																					
12-lead ECG	X					X						X									X	X b
Review of Inclusion/Exclusion Criteria	X	X																				
Complete Physical Exam c	X																					
Symptom directed physical exam c (as needed)		X	X	X	X	X	X	X		X		X		X		X		X		X	X	X
Vital Signs	X	X	X	X	X	X	X	X		X		X		X		X		X		X	X	X
Height	X																					
Weight	X	X	X	X	X	X		X		X		X		X		X		X		X	X	X
Adverse Events	X	X	X	X	X	X	X	X		X		X		X		X		X		X	X	X
Concomitant Medications	X	X	X	X	X	X	X	X		X		X		X		X		X		X	X	X
Randomization		X					X															

Period	Screen	Treatment																			Follow-up	
Visit	1	2	3	4	5	6	7	8	9	10	11	12	13	14	15	16	17	18	19	20	PTx a	ET
Week		0	2	4	6	10	11	14	17	20	23	26	30	34	38	42	46	50	54	58		
Study Day	-30 to -1	1	15	29	43	71	78	99	120	141	162	183	211	239	267	295	323	351	379	407		
Visit Window			±3	±3	±3	±2	±3	±5	±5	±5	±5	±5	±5	±5	±5	±5	±5	±5	±5	±5	±3	±3
Study Drug Dispensing		X		X			X	X		X		X		X		X		X				
Colonoscopy/Flexible Sigmoidoscopy with biopsy	X d					X															X	
Investigator Endoscopic Value (0,1,2,or 3) e	X					X															X	
Mayo Score (Partial) f		X	X	X	X		X	X		X		X		X		X		X				X
Mayo Score (Complete)	X					X															X	
eDiary instruction & review g	X	X	X	X	X	X	X	X		X		X		X		X		X			X	
Stool for C. diff toxin, pathogenic E. coli , Salmonella spp, Shigella spp, Campylobacter spp or Yersinia spp testing	X																					
Stool O&P h	X																					
Stool microbiome	X					X						X									X	
Fecal MMP-9	X					X						X									X	
Fecal Lactoferrin, Calprotectin	X					X						X									X	

Period	Screen	Treatment																			Follow-up		
		2	3	4	5	6	7	8	9	10	11	12	13	14	15	16	17	18	19	20	PTx a	ET	
Visit	1																						
Week		0	2	4	6	10	11	14	17	20	23	26	30	34	38	42	46	50	54	58			
Study Day	-30 to -1	1	15	29	43	71	78	99	120	141	162	183	211	239	267	295	323	351	379	407			
Visit Window			±3	±3	±3	±2	±3	±5	±5	±5	±5	±5	±5	±5	±5	±5	±5	±5	±5	±3	±3		
Urine drug screen i	X																						
Urinalysis	X	X				X														X			
Pregnancy Test j	X	X		X	X	X		X	X	X	X	X	X	X	X	X	X	X	X	X	X	X	
TB k	X																						
Chest x-ray l	X																						
HBV, HCV, HIV screening m	X																						
HBV DNA monitoring (Japan) n				X	X	X		X	X	X	X	X	X	X	X	X	X	X	X	X	X		
HBV monitoring (other regions) n						X				X				X				X		X			
Hematology	X	X	X	X	X	X		X		X		X		X		X		X		X	X	X	
Chemistry	X	X	X	X	X	X		X		X		X		X		X		X		X	X	X	
Lipid profile (fasting) o		X				X						X								X		X	
CRP	X	X	X	X	X	X		X		X		X		X		X		X		X	X	X	
Serum immunoglobulin		X		X		X						X								X	X	X	
Blood TCR/BCR repertoire samples p		X		X		X						X								X			
Plasma biomarker sample		X		X		X						X								X			

[figure not shown]

Period	Screen	Treatment																				Follow-up		
		2	3	4	5	6	7	8	9	10	11	12	13	14	15	16	17	18	19	20	PTx a	ET		
Visit	1																							
Week		0	2	4	6	10	11	14	17	20	23	26	30	34	38	42	46	50	54	58				
Study Day	-30 to -1	1	15	29	43	71	78	99	120	141	162	183	211	239	267	295	323	351	379	407				
Visit Window			±3	±3	±3	±2	±3	±5	±5	±5	±5	±5	±5	±5	±5	±5	±5	±5	±5	±3	±3			
Serum biomarker sample		X		X		X						X								X				
Blood transcriptome sample		X		X		X						X								X				
PK collection (sparse) g				X		X						X								X				
vfPBMC c		X		X		X						X								X				
PK substudy d				X																				
CCI																								
HRQoL Surveys a		X				X						X								X				
HCRU questionnaire		X	X	X	X	X	X	X		X		X		X		X		X		X				

- a The Post Treatment (PTx) visit should occur 30 days after the last dose of study drug. Only subjects who roll over into the LTE study (GS-US-418-3899) will not complete PTx assessments.
- b For subjects who terminate prior to Week 10
- c A complete physical examination (PE) including, vital signs, body weight, and height will be performed at screening. (GU exam at investigator discretion). A symptom directed PE may be done as needed at other time points.
- d Diary data and other eligibility criteria should be reviewed prior to scheduling endoscopy. Perform the screening colonoscopy/flexible sigmoidoscopy within 2 weeks of Day 1 (Day -14 to -1). Subject should meet stool frequency and rectal bleeding requirements based on diary data prior to endoscopy performance.
- e The investigator (ie, local endoscopist) should enter in an endoscopic subscore (0, 1, 2, or 3) based on the Mayo Clinic Scoring System endoscopic scale (Appendix 4); this will be entitled the Investigator Endoscopic Value. The locally read score entered may not be used for eligibility or Mayo Clinic Score calculation purposes, and is not a substitute for the centrally read score, but is collected solely for exploratory purposes.
- f Includes all parts of the Mayo score except endoscopy
- g Subjects should begin filling out the eDiary the day after their initial screening visit and continue to fill it out throughout the remainder of the study.
- h Stool samples should be collected to rule out infectious causes when disease worsens.
- i Positive cocaine test disqualifies subject; positive amphetamines, barbiturates, benzodiazepines, and opioids require medical monitor review.
- j All females meeting the childbearing potential criteria must have a serum pregnancy testing at screening and a urine pregnancy test must be completed in clinic every 4 weeks at a minimum. If any pregnancy test is positive, study drug should be immediately interrupted and the subject should have a serum pregnancy test in clinic.

- k Proof of no active or untreated latent TB at screening. Subjects who are diagnosed with latent TB at screening must initiate an adequate course of prophylaxis as per local standard of care for a minimum of 4 weeks prior to randomization. Subject may initiate study drug dosing only after consultation with the medical monitor.
- l Chest x-ray (views as per local guidelines) taken at screening or within the 3 months prior to screening (with the report or films available for investigator review) without evidence of active or latent TB infection
- m Hepatitis B surface Ag, surface Ab and core Ab, reflex HBV DNA, Hepatitis C Ab, reflex HCV RNA, HIV Ag/Ab, reflex HIV 1/2 Ab at Screening (Section 6.2.1).
- n In Japan, subjects with negative HBsAg, positive HBcAb and/or positive HBsAb at Screening require HBV DNA monitoring every 4 weeks in accordance with local guidelines (Section 6.2.1). In other regions, subjects with negative HBsAg and positive HBcAb require HBV DNA monitoring every 3 months in accordance with local guidelines (Section 6.2.1)
- o Fasting means no food or drink, except water, for 8 hours
- p TCR: T-cell receptor; BCR: B-cell receptor
- q This PK sample at Weeks 10 and 58 are collected at pre-dose (within 2 hours prior to dosing). The PK sample at Week 4 is collected post-dose (at least 30 minutes and up to 3 hours after study drug dosing). For this visit, it is preferred that study drug dosing is in clinic. The PK sample at Weeks 26 can be collected at any time without regard to dosing. For these visits, the time of dose taken on the day of and the dose taken prior to the PK sample being drawn will be noted in the eCRF.
- r vfpBMC collection at US and Canadian sites only.
- s Subjects who consent to optional PK substudy will have an additional plasma PK sample at any single visit from Week 2 and 10, collected pre-dose and at 0.5, 1, 2, 3, 4 and 6 hours after supervised dosing in the clinic. For all visits with PK sampling, the time of dose taken prior to and on the day of visit will be noted in the eCRF
- t [REDACTED]
- u HRQoLs include SF-36, WPAI, EQ-5D, IBDQ

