#### 3.5.2. Study Drug Discontinuation Considerations

The Gilead Medical Monitor should be consulted prior to study drug discontinuation when medically feasible.

Study drug must be permanently discontinued in the following instances:

- Any opportunistic infection
- Any serious infection that requires antimicrobial therapy or hospitalization, or any infection that meets SAE reporting criteria
- Febrile neutropenia (temperature  $> 38.3^{\circ}\text{C}$  or a sustained temperature of  $> 38^{\circ}\text{C}$  for more than one hour) with absolute neutrophil count of  $< 1,000/\text{mm}^3$
- Symptomatic anemia (eg, signs/symptoms including pallor, shortness of breath, new heart murmur, palpitations, lethargy, fatigue ) with hemoglobin  $< 7.5 \text{ g/dL}$  , or if transfusion is indicated regardless of hemoglobin value
- Complicated herpes zoster infection (with multi-dermatomal, disseminated, ophthalmic, or CNS involvement)
- Evidence of active HCV during the study, as evidenced by HCV RNA positivity
- Evidence of active HBV during the study, as evidenced by HBV DNA positivity

- Unacceptable toxicity or toxicity that, in the judgment of the investigator, compromises the subject's ability to continue study-specific procedures or is considered to not be in the subject's best interest
- Subject request to discontinue for any reason
- Subject noncompliance
- Pregnancy during the study; refer to Section 7.7.2.1
- Discontinuation of the study at the request of Gilead, a regulatory agency or an institutional review board or independent ethics committee (IRB/IEC)
- Subject use of prohibited concurrent therapy *may* trigger study drug discontinuation; consultation should be made with the Gilead Medical Monitor.
- Laboratory Criteria: After becoming aware of any of the below described abnormal laboratory changes occurring at any one time, an unscheduled visit (ie, sequential visit) should occur to retest within 3 to 7 days (except creatinine, which should be retested 7 to 14 days apart).

— 2 sequential neutrophil counts < 750 neutrophils/mm^3 (SI: < 0.75x10^9 cells/L)

— 2 sequential platelet counts < 75,000 platelets/mm^3 (SI: < 75.0x10^9 cells/L)

— 2 sequential aspartate aminotransferase (AST) or alanine aminotransferase (ALT) elevations > 3x the upper limit of normal (ULN) and at least one of the following confirmed values:

- total bilirubin >2x ULN

- INR > 1.5

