- TB Assessment– Must have negative QuantiFERON® test (or centrally reported equivalent assay) during screening, and negative chest x-ray within 3 months of or during screening for those with no evidence or history of TB. Positive or negative results must not be repeated. An indeterminate result should be repeated once and the second result (if positive or negative) will be accepted. Two sequential indeterminate results constitute a screen failure. Subjects with previously treated or latent TB require sponsor approval (See inclusion criterion 8 for details). Subjects who are diagnosed with latent TB at screening must initiate an adequate course of prophylaxis as per local standard of care for a minimum of 4 weeks prior to randomization. Subject may initiate study drug dosing only after consultation with the Gilead medical monitor.
- Obtain blood samples (reference Study Procedure Table in [Appendix 2](#))
  - **HCV Screening Guidelines**
    - Subjects with positive HCV antibody at Screening require reflex testing for HCV RNA. Subjects with HCV RNA  $\geq$  lower limit of quantification (LLOQ) at Screening will be excluded. Subjects with positive HCV antibody but HCV RNA  $<$  LLOQ are eligible.
  - **HBV Screening and Surveillance Guidelines**
    - Subjects with positive HBV surface antigen (HBsAg) at Screening are excluded.
    - Subjects who are positive for HBV surface antibody (HBsAb), but negative for both HBsAg and HBV core antibody (HBcAb) at Screening are eligible.

- Subjects with positive HBcAb require reflex testing for HBV DNA. Subjects with HBV DNA  $\geq$  LLOQ at Screening will be excluded. Subjects with positive HBcAb and HBV DNA  $<$  LLOQ are eligible, but will require ongoing HBV DNA monitoring every 3 months during this study. These subjects may require prophylactic treatment per investigator discretion in accordance with local guidelines/standard of care.
- In Japan and where required by local guidelines, subjects with positive HBcAb and/or positive HBsAb will require reflex testing for HBV DNA at Screening. Subjects with positive HBcAb and/or HBsAb but with HBV DNA  $<$  LLOQ at Screening are eligible for the study. These subjects will require ongoing HBV DNA monitoring every 4 weeks in accordance with local guidelines during this study.
- Any subject who has HBV DNA  $\geq$  LLOQ during the study will be discontinued (reference Section 3.5.2).

— **HIV Screening Guidelines**

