- Subjects who have HIV infection, regardless of virologic status, are excluded from the study.
- Obtain blood sample for serum pregnancy test (for females of childbearing potential only)
- Obtain stool sample (reference Study Procedure Table in [Appendix 2](#))
  - A stool sample will be obtained for culture for pathogenic bacteria, ova and parasite evaluation, and *C. difficile* toxin assay during screening for the purposes of determining eligibility.
- Obtain urine sample (reference Study Procedure Table in [Appendix 2](#))
- Obtain urine sample for urine drug screen (reference Study Procedure Table in [Appendix 2](#))

A single retest of screening labs is permitted only if there is reason to believe the retest value will be within accepted parameters, or if the initial value was either due to a sample processing error or an extenuating circumstance.

Subjects meeting all of the inclusion criteria and none of the exclusion criteria will return to the clinic within 30 days after screening for randomization into the study. Subjects may be randomized more than 30 days after initial screening if they receive permission from the Gilead Medical Monitor. If the subject does not begin the treatment within this 30-day window, specific screening evaluation procedures may need to be repeated at the direction of the Gilead Medical Monitor. No more than one repeat screening visit is allowed for each subject, unless prior written approval has been provided by the Sponsor.

From the time of obtaining informed consent through the first administration of investigational medicinal product, record all SAEs, as well as any AEs related to protocol-mandated procedures on the adverse events eCRF. All other untoward medical occurrences observed during the screening period, including exacerbation or changes in medical history are to be captured on the medical history eCRF. See Section 7 Adverse Events and Toxicity Management for additional details.

### 6.2.2. Day 1

The following tests and procedures must be completed prior to randomization and dosing/dispensing:

- Review inclusion/exclusion criteria and other protocol restrictions
- Symptom directed PE including body weight
- Obtain body weight and vital signs (resting blood pressure, respiratory rate, pulse and temperature)
- Review AEs and concomitant medications
- Review e-Diary reports for compliance and scores – remind subjects of diary instructions at every visit

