#### 6.4.3.1. Clinical Laboratory Evaluations

The hematology, serum chemistry, coagulation laboratory, and stool analyses will be performed at a central laboratory. Reference ranges will be supplied by the central laboratory and will be used by the investigator to assess the laboratory data for clinical significance and pathological changes.

Blood samples will be collected by venipuncture (or optional indwelling catheter for PK sampling days) in the arm at the time points indicated in the Study Procedures Table ([Appendix 2](#)). In addition, urine samples for the clinical laboratory assessments will be collected. An overnight fast (no food or drinks, except water) of at least 8 hours will be required prior to collection of blood samples for lipid testing.

A stool sample should also be collected at any time during the study for culture for pathogenic bacteria, ova and parasites, and *C. diff* toxin assay when a subject becomes symptomatic, including worsening or return of disease activity.

Refer to [Appendix 7](#) for table of clinical laboratory tests.

Laboratory values outside the normal range will be flagged and clinical relevance will be assessed by the investigator. More frequent sampling as well as additional tests may be performed as deemed necessary by the investigator.

Note that in the case where clinically significant laboratory test results are a potential reason for discontinuation from the study drug and/or withdrawal from the study, retesting of the affected parameter(s) should be prompt (within 3 to 7 days [except creatinine, which should be retested 7 to 14 days apart]).

The details of sample handling and shipment instructions will be provided in a separate laboratory manual.

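### Outside Japan, the procedures table leaves 112 days (Week 34 to Week 50) without an HBV DNA test that the protocol requires every three months

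*Protocol*

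**What the plan says.** Protocol Section 6.2.1 states that "Subjects with positive HBcAb require reflex testing for HBV DNA". Those at or above the LLOQ are excluded. Those below it may enter, but "will require ongoing HBV DNA monitoring every 3 months during this study". Footnote n to Appendix 2 repeats the interval for regions other than Japan: these subjects "require HBV DNA monitoring every 3 months in accordance with local guidelines". Footnote m places the first test at Screening ("Hepatitis B surface Ag, surface Ab and core Ab, reflex HBV DNA").

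In the Appendix 2 table, the other-regions row is marked at Weeks 10, 20, 34, 50 and 58 and nowhere else. The Japan row, which implements a four-weekly rule, is marked at every scheduled visit from Week 14 to Week 58.

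The result carries a consequence. Section 3.5.2 lists "Evidence of active HBV during the study, as evidenced by HBV DNA positivity" among the reasons for permanent discontinuation, and Section 6.2.1 requires discontinuation when HBV DNA reaches the LLOQ.

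**The concern.** The text fixes a maximum spacing, and the table is where sites look to see which visit needs which sample. If the marks are further apart than the text allows, a site that follows the table exactly departs from Section 6.2.1 without noticing.

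What is at stake is the timing of a safety check that triggers a mandatory stop, in subjects with past HBV exposure who are taking an immunomodulating drug. No efficacy endpoint or test depends on it.

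**Working it through.** **Inputs.** Study days and visit windows come from the Appendix 2 header: Week 10 = Day 71 (±2), Week 20 = Day 141 (±5), Week 34 = Day 239 (±5), Week 50 = Day 351 (±5), Week 58 = Day 407 (±3). Screening runs from Day -30 to Day -1. The protocol gives no day count for three months; I take about 91 days.

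**Formula.** The nominal gap is the later day minus the earlier day. The range within windows is the nominal gap minus and plus the sum of the two windows. SAP Section 3.8.1.1 has no Day 0, so a screening test on Day -k precedes Day 71 by k + 70 days.

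| Interval | Nominal gap (days) | Range within windows | Against 91 days |
|---|---|---|---|
| Screening to Week 10 | 1 + 70 = 71 to 30 + 70 = 100 | 69 to 102 | can exceed; nominally over when k > 21 |
| Week 10 to 20 | 141 - 71 = 70 | 63 to 77 | complies |
| Week 20 to 34 | 239 - 141 = 98 | 88 to 108 | can exceed, but can be met |
| Week 34 to 50 | 351 - 239 = 112 | 102 to 122 | cannot comply |
| Week 50 to 58 | 407 - 351 = 56 | 48 to 64 | complies |

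**Excess for Week 34 to 50.** 112 - 91 = 21 days nominally; 102 - 91 = 11 and 122 - 91 = 31 days at the edges of the windows.

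**Screening.** Section 6.2.1 adds that "Subjects may be randomized more than 30 days after initial screening if they receive permission from the Gilead Medical Monitor". That would lengthen the first interval unless the screening tests are repeated.

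**Is it a table-reading artefact?** In the protocol table every post-screening study day equals 7 × week + 1, and the other-regions, Japan and Hematology rows line up with the same columns. SAP Appendix 1 shows the same other-regions marks at Weeks 10, 20, 34 and 50. Its last mark falls one column to the right of Week 58 in the extracted text, so I do not rely on the SAP copy for that visit. The Week 34 to 50 gap does not depend on it.

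**The case against.** Four points can be made for leaving the table alone.

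1. **The rule is already in front of the site.** The row carries footnote n, which states the interval, and Section 6.4.3.1 says "More frequent sampling as well as additional tests may be performed as deemed necessary by the investigator". This stands in part: the marks do not prevent compliance. But a discretionary allowance does not schedule a required test.

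2. **Three months can be read as a rate.** Five post-screening tests over 406 days (Day 1 to Day 407) is one per 406 / 5 = 81 days, which is often enough on average. An average does not fit monitoring meant to catch reactivation and stop the drug. There the longest gap matters, and short gaps elsewhere do not offset it.

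3. **Footnote n defers to local guidelines.** It does, but the Section 6.2.1 sentence for these subjects sets the interval without that qualifier. The reference to local practice there concerns prophylaxis. Nothing in either document allows 16 weeks.

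4. **The subjects are not unmonitored.** Chemistry is drawn at Week 42, and Section 3.5.2 has transaminase stopping rules. Screening HBV DNA was below the LLOQ and prophylaxis is possible. All of this stands and is why the point is minor. It does not replace the HBV DNA test the protocol asks for.

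**Conclusion.** The schedule and the text disagree. One of the five intervals, Week 34 to Week 50, cannot meet the three-month rule at any permitted timing of the marked visits. Two others, Screening to Week 10 and Week 20 to 34, can exceed 91 days but need not, so I do not count them as breaches.

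The conclusion rests on reading three months as a maximum gap of about 91 days. The shortest permitted gap of 102 days leaves room for any ordinary reading of that interval.

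This is a minor point. It concerns only HBcAb-positive subjects outside Japan who reach the later part of the Maintenance Study, and the documents do not say how many there are. Sample size, alpha, power and the efficacy analyses are unaffected.

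**What to change.** Add an HBV DNA mark at Week 42 (Day 295) in the other-regions row of Protocol Appendix 2, and make the same change in SAP Appendix 1. The gap becomes 295 - 239 = 56 and 351 - 295 = 56 days, each 46 to 66 within windows. Hematology and chemistry are already drawn at Week 42, so the cost is one assay per affected subject, with no extra visit or blood draw. This is better than moving the Week 50 test to Week 46: Week 34 to 46 is 323 - 239 = 84 days but up to 94 within windows, and Week 46 has no routine hematology or chemistry.

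Under Section 9.2.1 the change needs documented IRB/IEC approval, and about 500 sites are planned, so it is best bundled with another amendment. Until then, a note to sites restating footnote n and asking for a test at Week 42 would cover the gap.

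Optionally, marks at Week 26 and at Week 4 or Week 6 would also bring the other two intervals under 91 days at every permitted timing within the 30-day screening period, for three added assays in all. That is a preference and is not needed to remove the breach.
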